### **Binary outcomes such as HIV testing:**

The percentage of participants who report routine HIV testing over a 12-month period will be compared between the intervention arms (GC and the Control condition). Five assessments will occur at 1 month (visit window  $\pm$  1 month), 3 months ( $\pm$  1 month), 6 months ( $\pm$  1 month), 9 months ( $\pm$  1 month), and 12 months ( $\pm$  1 month). Repeated-measures analyses for HIV testing will be implemented by performing a generalized estimating equations (GEE) analysis via the SAS GENMOD Procedure (version 9.4; SAS Institute, Cary, NC) with an exchangeable correlation structure for the repeated measures within participant (binomial-logit model). The statistical model will include three predictors (intervention arm, time on study and the statistical interaction between intervention arm and time on study). The statistical model will provide estimates of the percentages of participants reporting HIV testing (plus 95% confidence intervals) by intervention arm and time on study. The model-based estimates are unbiased with unbalanced and missing data, so long as the missing data are non-informative (missing completely at random, MCAR). A P value  $\leq 0.05$  will be considered statistically significant for the main effects (intervention and time on study) and for the intervention by time on study interaction effect from the repeated measures analysis. **The statistical test for interaction between time on study and intervention arm will be the primary overall hypothesis test to determine whether HIV testing in the intervention groups changed in significantly different ways during follow-up (i.e., different temporal patterns over time).** If HIV testing rates in the two intervention groups are consistently different or similar (i.e., no statistical interaction) then the main effect test for intervention will be used as the primary test of intervention efficacy. If a significant interaction is detected, then Wald chi-square tests will be used to compare the differences between the model-based HIV testing estimates at each time interval and to compare differences over time within each intervention arm. Specific statistical tests will be done within the framework of the generalized linear model. All statistical tests will be 2-sided and unadjusted for multiple comparisons.

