The primary assessment for a difference between intervention arms for 'frequent tester' rates will be a two-sided Z-test for independent proportions with pooled variance. Confidence intervals (95%) will also be reported for the observed difference between the GC and control arms in 'frequent tester' rates. The same analysis plan described above will be used for the other primary outcomes that as binary (i.e., STI testing, PrEP awareness).

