We will use SurveyGizmo to collect YMSM's data. *At baseline, participants will be logged into the SurveyGizmo assessment by site study staff. For follow-up assessments, participants will receive a unique link which will allow them to complete the surveys in multiple sittings or to resume a survey that has timed out or been closed.* Online surveys allow participants to complete the survey at a convenient location, circumvent barriers (e.g., scheduling, transportation) present in interviewer-administered or phone-based interviews, and decrease social desirability. To maximize completion rates, participants will receive email and/or text reminders that a survey is available. Although we will employ recommended strategies to avoid loss to follow-up, we project a conservative attrition of 20%. In the pilot study, we achieved >80% retention using the approaches proposed here.

Secondary objective:

- **Phase 2a: Enrolling and Training of Mystery Shoppers**  
We will enroll and train 10-15 mystery shoppers per city to conduct the mystery shopper assessments. This approach follows best practices indicating that youth involvement is vital when designing relevant and appropriate HIV interventions for the target population. As study staff, we will work with the ATN site in each city to enroll HIV-negative YMSM (ages 18-24) who are interested in serving as mystery shoppers. We will employ a stratified purposive sampling strategy to ensure age and racial/ethnic diversity across mystery shoppers. Of the 10-15 mystery shoppers in each city, we will attempt to recruit diversity in age and race/ethnicity. Mystery shoppers will be 18 to 24 years old (inclusive).
- **Phase 2b: Site Visits**  
Based on feedback from agency directors in our original study, we will send all agency directors a letter informing them of their site's selection for the study before the mystery shopper visits and contact information to reach the research PIs if they have questions about the procedures. Shoppers will be instructed to report that they do not have income or health insurance and do not possess any proof of identification. In so doing, we will be able to ascertain whether these would be potential barriers to testing at a given location and determine the lowest possible fees that would be charged to a YMSM.
- **Phase 2c: Integration of Scores into GC Console**  

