## 4.0 ELIGIBILITY AND SCREENING

### 4.1 Primary Objective (RCT): Inclusion Criteria

- *Assigned male sex at birth and currently identifies as male*

- *Aged 15 to 24 years (inclusive) at time of screening*
- *Self-report as HIV-negative or sero-status unaware*
- *Speak and read English*
- *Not be on PrEP at time of enrollment*
- *Report having consensual anal sex with a male partner in the prior 6 months and/or report having not received HIV testing in prior 6 months*
- *Reside in Philadelphia, Houston, or Atlanta*
- *Access to internet*

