### 6.1.2 On-study Evaluations/Measures

- *HIV Testing:* Follow-up surveys will repeat the HIV testing questions in each follow-up survey. The HIV testing outcome will be: the proportion of MSM tested for HIV two or more times at least 3 months apart in the 12-month follow-up period (“frequent tester”). As an additional analysis, we will also examine the proportions of participants who receive one HIV test.
  - Among self-reported newly diagnosed HIV+ cases, we will measure their linkage and engagement with appropriate medical care after initial diagnosis using criteria employed in prior ATN protocols with youth. We will define linkage as an HIV-related medical visit within 45 days of referral, and engagement as a second HIV-related medical visit within 16 weeks of initial visit. Onset of ART initiation, self-reported adherence to ART, and viral suppression are exploratory indicators, as we recognize that our follow-up period may not be a sufficient amount of time to see these changes.
- *STI Testing:* The STI testing outcome is defined as the proportion of YMSM tested for STIs at least once in the 12-month follow-up period. We will ask participants what STIs they have been tested for, the anatomic sites where they were tested, the date of their most recent STI test (if known), and whether a medical provider had diagnosed them with an STI. In the follow-up surveys, we will ask participants whether they had been tested for STIs in the past 3 months (for the 1-month follow-up survey, we ask about the past 30 days). If STI testing is reported, we will ask participants to indicate what tests they received, and whether they were diagnosed with an STI by a medical provider.
- *PrEP Use:* At each follow-up assessment, PrEP-eligible HIV-negative YMSM (per CDC guidelines) will be asked whether they have begun using PrEP. We will also ascertain if a provider recommended PrEP and/or were offered a prescription for PrEP.
 

*Site Evaluations:* Across both trial arms, YMSM who report testing in the prior 3 months will complete self-evaluation forms of their testing experiences to assess comfort, quality, and concerns after visiting a site for HIV/STI testing and PrEP prevention services. The assessment form is the same form used by the mystery shoppers. We will use these data to update the WebApp and to send aggregate data of YMSM's satisfaction with services to agencies biannually.

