#### 10.4 Missing Data

Several procedures will be used to conduct data analysis when data for either outcomes or covariates are missing. The first step will be to assess the extent and pattern of missing data. If data are missing for only a few cases, then data analysis will be conducted only on study participants with complete data. However, when such a strategy would result in loss of data from a substantial proportion of participants, or if this approach would lead to biased or inaccurate results, then some form of imputation will be performed. The form of imputation used will depend on the nature of the data that are missing. For example, data that are collected repeatedly might be imputed using the "last value carried forward" method; and in some instances, interpolation between neighboring points might also be used.

When the primary endpoint is missing, one data analysis will be conducted using only cases with the endpoint. Subsequent analysis will be done where missing endpoints are imputed. Hot-deck imputation or regression imputation may also be used in this context.

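### The primary binary analyses rest on MCAR or on complete cases, so the frequent-tester comparison is unprotected if dropout linked to testing history differs by arm

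*Combined protocol and SAP*

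**What the plan says.** All references are to the combined protocol and SAP.

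- **Section 2.4, binary outcomes.** The repeated-measures analysis of HIV testing is a GEE with exchangeable correlation: "The statistical model will include three predictors (intervention arm, time on study and the statistical interaction between intervention arm and time on study"). Its stated condition is: "The model-based estimates are unbiased with unbalanced and missing data, so long as the missing data are non-informative (missing completely at random, MCAR"). The same plan serves STI testing and PrEP awareness. For continuous outcomes the same section claims the weaker MAR condition.
- **Section 2.4, frequent testers.** "The primary assessment for a difference between intervention arms for 'frequent tester' rates will be a two-sided Z-test for independent proportions with pooled variance". No rule for missing endpoints is given there. Section 6.1.2 defines the endpoint as "the proportion of MSM tested for HIV two or more times at least 3 months apart in the 12-month follow-up period".
- **Section 10.4.** "When the primary endpoint is missing, one data analysis will be conducted using only cases with the endpoint". Then: "Subsequent analysis will be done where missing endpoints are imputed". The methods named are last value carried forward, interpolation, hot-deck and regression imputation, all offered as possibilities. No imputation model or variables are given.
- **Section 10.3.1.** The general framework is a maximum-likelihood GLMM with covariates, and the exchangeable GEE is there for robustness. A logistic model for having tested at least once adjusts for baseline values.
- **Section 3.1, Phase 1c.** "we project a conservative attrition of 20" per cent.
- **Section 4.1.** Men qualify by recent anal sex "and/or report having not received HIV testing in prior 6 months", so recent testers and men not recently tested are both enrolled.

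**The concern.** The outcome named as primary for the trial has the least protected analysis. Prior testing is likely to predict later testing. It is asked about at screening and again at baseline (sections 4.1 and 6.1.1), yet neither the three-predictor GEE nor the Z-test uses it, and neither uses earlier survey reports to account for men who leave.

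The arms differ in what they offer. GC men see tailored content on testing, retailored after each survey, while control men see a site locator. Men with little interest in testing could therefore leave one arm more readily than the other. The men remaining would then differ in testing history between arms, and a difference in frequent-tester rates could appear, grow or shrink for reasons unrelated to GC.

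**Working it through.** **Inputs.** From the documents: 240 per arm (5.3), 20% attrition (3.1), and two-sided 0.05, 80% power, a 13-point difference and 400 participants (10.2.1). Not in the documents, so assumed: the control frequent-tester rate, the mix of testing histories, the rates within each history stratum, and retention by stratum and arm.

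**1. The plan's own figure.** Per arm, n = [1.960√(2p̄(1−p̄)) + 0.8416√(p₁(1−p₁)+p₂(1−p₂))]² / d². With p₁ = 0.25, p₂ = 0.38, p̄ = 0.315 and d = 0.13: (1.960 × 0.6569 + 0.8416 × 0.6505)² / 0.0169 = 199.2. That is 200 per arm, or 400 in total. The stated 400 therefore reproduces at a control rate near 25% (392 at 24%, 406 at 26%), and 25% is used below as the overall rate.

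**2. Exact bias of a completers-only test, no true effect.** Put half the men in each history stratum, with rates p_H and p_L and retention r_H and r_L. The observed rate is (r_H p_H + r_L p_L)/(r_H + r_L). Every pattern below averages 80% retention, so 240 × 0.8 = 192 per arm. With d the bias, type I error = 1 − Φ((1.96·SE₀ − d)/SE₁) + Φ((−1.96·SE₀ − d)/SE₁), where SE₀ is pooled and SE₁ unpooled.

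Example: rates 40%/10%, GC retention 90/70, control 80/80. GC shows (0.9 × 0.40 + 0.7 × 0.10)/1.6 = 26.9% and control 25.0%. The bias is 1.9 points and type I error 0.062 + 0.009 = 7.0%.

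| Rates, recent testers / others | GC retention | Control retention | Bias (points) | Type I error |
|---|---|---|---|---|
| 35% / 15% | 90/70 | 90/70 | 0.0 | 5.0% |
| 35% / 15% | 90/70 | 80/80 | +1.25 | 5.9% |
| 35% / 15% | 90/70 | 70/90 | +2.5 | 8.7% |
| 40% / 10% | 90/70 | 90/70 | 0.0 | 5.0% |
| 40% / 10% | 90/70 | 80/80 | +1.9 | 7.0% |
| 40% / 10% | 90/70 | 70/90 | +3.75 | 13.5% |

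Swapping the arms reverses the sign. Add a true 13-point effect to both strata at 35%/15%. The opposite-link pattern then gives 39.25 − 23.75 = 15.5 points (power 91%), or 36.75 − 26.25 = 10.5 points (power 60%) with the arms swapped. Without bias, 192 per arm gives 78.5% power.

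**3. Simulation of the frequent-tester test.** Set-up: 240 per arm, five surveys, half the men recently tested (log-odds +1.2 for testing), random-intercept SD 1.0 or 2.2, frequent tester taken as at least two of the four 3-month reports, 4,000 null trials per scenario.

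- GC loses 8% of prior testers and 33% of non-testers, control 21% of both: +1.3 to +2.2 points, type I error 6.1–7.9%.
- Same GC pattern, control loses 30% of prior testers and 10% of non-testers: +2.3 to +3.9 points, 8.8–13.6%.
- GC men with no test at the last survey leave more often: +2.2 to +2.8 points, 7.7–10.1%.

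**4. The GEE.** In the same three scenarios, month-12 bias was +0.5 to +1.1, +0.9 to +1.9 and at most 0.3 points. A separate 60-trial simulation of the opposite-link pattern gave about +2 points at the last survey (Monte Carlo error about 0.5).

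**5. After adjustment.** In the step 3 simulations, weights estimated by arm, prior testing and last report brought frequent-tester bias to about 0.1 point and type I error to 4.4–5.0%. Earlier reports matter as well as history. In a deliberately extreme pattern of dropout on the last report, opposite by arm, standardising for baseline history alone cut a 9.5-point bias only to 8.3. A second run weighted on arm and last report went from 9.2 to 0.05.

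**The case against.** Several points on the other side stand.

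- **There are other analyses.** A reader might infer that the frequent-tester result rests on case-only data alone. It does not. Section 10.4 adds an imputed analysis and calls for imputation where a case-only approach would mislead. But that analysis comes later, its method is left open, and only single imputation is named, which understates uncertainty. The GLMM in 10.3.1 is valid under MAR if correctly specified, but it does not protect the Z-test, and sections 2.4 and 10.3.1 disagree on whether GLMM or GEE leads.
- **MCAR is not strictly required.** The GEE's mean model contains arm and time, so missingness depending only on those is tolerated. Its bias under dropout on the last report was negligible.
- **The GEE harm is small.** The detectable differences in 10.2.1 (8.8 and 11.3 points) divided by 2.80 imply standard errors of about 3.1 to 4.0. A bias averaged over surveys of 0.4 to 0.7 points, as in the first scenario, then gives a main-effect type I error of about 5.1–5.6%. No reliable figure is available for the interaction test.
- **Case-only need not mean completers only.** A man who reported two qualifying tests before leaving has the endpoint. In a simulation that counted such men, bias of +1.3 to +3.4 points fell to +0.9 to +2.7. It was reduced, not removed.
- **The mechanism is assumed.** Surveys are the same in both arms (5.4.1), compensation is not arm-specific (8.2) and participant blinding is intended (3.4). Losing interest in a website is not the same as leaving paid surveys.

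**Conclusion.** The point holds as a conditional weakness. The primary binary analyses rely on MCAR or complete cases, and the back-up is too loosely specified to count as protection. With 20% attrition and a history–dropout link that differs by arm, the frequent-tester difference is off by roughly 1 to 4 points, against a target of 13, with type I error of about 6–14%. The GEE is off by about 0.5 to 2 points at month 12. The strata rates and retention splits behind these figures are assumptions.

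A reader might go further and infer that the efficacy estimate will be biased, or biased in favour of GC. The documents do not support that: they give no attrition by arm or by history, the direction could be either way, and a link that is the same in both arms gives no material bias. Nor do the results show that weighted GEE is the only remedy, since multiple imputation on the same variables would serve equally well.

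**What to change.** 1. **Sections 2.4 and 10.4:** make the primary binary analyses valid under MAR, by multiple imputation by arm or by inverse-probability weighting (weighted GEE, with the same weights for the frequent-tester comparison). Include arm, city, baseline HIV testing history, earlier survey testing reports, and arm-by-history and arm-by-last-report terms.
2. Replace the MCAR sentence with MAR given these variables.
3. Keep the unweighted GEE and the case-only Z-test as sensitivity analyses. Drop single imputation, such as last value carried forward, for the endpoint.
4. Name one lead model across sections 2.4 and 10.3.1.
5. Reconcile the end of section 8.4, which has interview data of withdrawn participants destroyed and left out of analysis, with section 2.4, which promises all data from everyone randomized. If the rule covers RCT surveys, the method lacks the data it needs for those men.

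**Cost:** SAP wording, a little more programming, and reliance on a response or imputation model. In the simulations, weighting changed the standard error of the frequent-tester difference by about −3% to +1%. That is a best case, because the weights used the variables that drove dropout.

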### 2.4 Study Hypotheses/Research Questions

- *Relative to the control condition, YMSM exposed to the GC intervention will report significantly greater increases in routine HIV/STI testing over a 12-month period. HIV testing will be the primary outcome for the trial.*
- *Relative to the control condition, YMSM exposed to the GC intervention will report increases in motivation around HIV testing (conceptualized as HIV/STI testing intentions, self-efficacy to engage in HIV/STI testing, and overcoming testing-related barriers).*
- *Relative to the control condition, YMSM exposed to the GC intervention will report significantly greater PrEP awareness and willingness to use PrEP).*

The primary analyses of the data from the Get Connected 2-parallel group randomized clinical trial will be performed according to the participants' original treatment assignment (i.e., intention-

to-treat analyses) and the inclusion of all data from all participants randomized in the final analysis.

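### Section 2.4 gives HIV testing two competing primary procedures and no rule for which decides; the null chance of a significant primary result is about 7–11% under one and 11–14% if either may be claimed

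*Combined protocol and SAP*

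**What the plan says.** Section 2.4 states: "HIV testing will be the primary outcome for the trial". Under its heading for binary outcomes it then sets out two analyses.

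- **GEE sequence.** A repeated-measures logit GEE is fitted to the surveys at months 1, 3, 6, 9 and 12, with arm, time and their interaction. The "interaction between time on study and intervention arm will be the primary overall hypothesis test". If there is no interaction, "then the main effect test for intervention will be used as the primary test of intervention efficacy". A P value of at most 0.05 "will be considered statistically significant for the main effects (intervention and time on study) and for the intervention by time on study interaction effect". The paragraph ends: "All statistical tests will be 2-sided and unadjusted for multiple comparisons".
- **Z-test.** The next paragraph says: "The primary assessment for a difference between intervention arms for" frequent-tester "rates will be a two-sided Z-test for independent proportions with pooled variance". It gives no significance level; 0.05 is taken here from Section 10.2.

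Section 6.1.2 defines the HIV testing outcome as "the proportion of MSM tested for HIV two or more times at least 3 months apart in the 12-month follow-up period". Section 10.2 sizes the trial on that proportion with a two-sample test of proportions.

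**The concern.** The two procedures analyse different quantities. The GEE uses testing reported at each of five surveys; the Z-test uses one 12-month value per participant. Both are labelled primary for the same outcome, and no section says which one decides or whether either may be claimed. The choice could therefore be made after the results are seen.

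The GEE sequence also has a problem of its own. It ranks its two tests, but it is not gatekeeping: failing the first test opens a second full 0.05 test instead of closing the procedure. And a significant interaction shows only that the arms followed different time courses. The hypothesis in Section 2.4 is directional (more testing under GC), and the plan does not say which visits, or which direction, would turn a significant interaction into a success.

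**Working it through.** **1. The plan's own sample size.** Section 10.2 gives 400 participants (200 per arm), 80% power, two-sided 0.05 and a 13-point difference, but no control rate. The pooled two-proportion formula is

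n per arm = [1.960·√(2p̄(1−p̄)) + 0.842·√(p₁(1−p₁)+p₂(1−p₂))]² / 0.13²

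With p₁ = 0.252, p₂ = 0.382 and p̄ = 0.317, this is (1.960×0.658 + 0.842×0.652)² / 0.0169 ≈ 200. By symmetry, 61.8% against 74.8% gives the same result. The plan's 400 is therefore reproduced at a control rate near 25% or near 62%, and both were used below.

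**2. Anchors by arithmetic, treating the tests as independent.**

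- GEE sequence, either direction: 0.05 + 0.95×0.05 = 1 − 0.95² = 9.75%.
- GEE sequence favouring GC, if an interaction never counts as success: 0.95×0.025 = 2.4%.

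**3. Null simulation.** The tests are correlated, so the rates were simulated.

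- *Data:* individual test dates from a Poisson process with gamma frailty and/or a share of never-testers, identical in both arms. Survey windows were the past month at month 1 and the past 3 months afterwards. Section 6.1.2 states the month-1 window for STI testing only; for HIV it is assumed.
- *Settings:* 12 in all. Four had a frequent-tester rate of 25–26% and five had 61–62%. Three had about 30% tested in month 1, echoing the pilot figure in Section 1.2.3, with frequent-tester rates of 53–82%. Within-person correlation was 0.05–0.73; Section 10.2 uses 0.25 and 0.75.
- *Size:* 240 per arm with 20% dropout (Section 3.1), and 200 per arm complete. That makes 24 runs of 10,000 trials, with Monte Carlo SE about 0.3 points. With dropout, the Z-test used 12-month completers (Section 10.4).
- *GEE:* exchangeable working correlation and robust covariance. Section 2.4 does not state the time coding or define the main effect, so five versions were run: categorical time with an averaged, refitted or month-12 main effect, and linear time with a refitted or time-0 main effect.

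A second simulation used a different data model, with complete data at 200 and 240 per arm and correlation 0 to about 0.74. Its last column below keeps only correlations near 0.25–0.75.

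| Null chance of a significant primary result | Main simulation | Second simulation | Second, correlation 0.25–0.75 |
|---|---|---|---|
| Z-test alone, either direction | 4.7–5.3% | each single test 4.6–5.6% | – |
| GEE sequence, either direction | 7.3–10.6% | 7.3–10.4% | 7.9–10.4% |
| GEE sequence or Z-test, either direction | 10.8–13.8% | 10.8–13.6% | 10.8–13.4% |
| GEE sequence, favouring GC (nominal 2.5%) | 1.3–5.5% | 1.1–5.5% | 1.4–5.1% |
| GEE sequence or Z-test, favouring GC | 3.1–7.3% | 3.0–7.2% | 3.0–6.3% |

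In the main simulation the GEE sequence runs at 9.1–10.6% when the main effect is averaged or refitted, and at 7.3–9.9% when it is the coefficient at one reference time.

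**4. The direction favouring GC, by success rule (main simulation).**

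| When a significant interaction counts for GC | GEE sequence | With Z-test |
|---|---|---|
| At least one visit significant for GC | 2.5–5.5% | 3.8–7.3% |
| The same, and no visit significant for control | 2.5–4.7% | 3.8–6.3% |
| Never | 1.3–2.7% | 3.1–4.6% |

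**5. How often the choice matters.** The two procedures disagree on significance in about 7–13% of null trials. At a 13-point difference (25 to 38%, or 62 to 75%; 240 per arm, 20% dropout; 4,000 trials per setting) they disagree in 15–19%, or 18–32% if the main effect is a coefficient at one reference time.

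**The case against.** The strongest reply is that the documents already point to the Z-test. Section 2.4 makes HIV testing primary, Section 6.1.2 defines it as the frequent-tester proportion, Section 2.4 assigns that proportion the Z-test, and Section 10.2 sizes the trial on it. On that reading the error is about 5%, and the interaction's primary label answers only a question about time patterns. The chain is real and is the best argument for choosing the Z-test. It does not settle the matter: no sentence gives the Z-test precedence, and the fallback main effect is itself called the primary test of efficacy.

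Other points stand in part.

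- The either-direction figures include significant interactions and results favouring control, so they are not rates of false claims for GC. Those rates are shown separately, and for the GEE sequence alone they straddle 2.5%.
- The top figures of 5.5% and 7.3% need near-zero within-person correlation and a rule under which any single favourable visit counts. Near 0.25–0.75 the upper ends are about 5.1% and 6.3%.
- Some of the disagreement at 13 points may reflect a difference in power between the procedures.
- Naming a test for HIV testing leaves STI testing and PrEP awareness with the same conflict, because Section 2.4 carries the plan over to them. It also leaves open how participants with incomplete follow-up are classified.

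**Conclusion.** The concern holds. Two procedures are called primary for the trial's primary outcome, on different quantities, and nothing ranks them.

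The GEE sequence as written roughly doubles the two-sided error in most codings. Allowing either procedure raises it further, and pushes the error favouring GC above 2.5% under every success rule tried. The GEE sequence alone does not inflate the error towards GC if a significant interaction never counts as success.

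The textual conflict is certain. The percentages are assumption-based ranges, because the plan gives no control rate, time coding, main-effect definition or rule for interpreting an interaction.

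**What to change.** Name one deciding test for HIV testing in Section 2.4, before any unblinded analysis. Suggested wording:

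> The single primary test of efficacy is the two-sided pooled Z-test at 0.05 comparing the 12-month frequent-tester proportion between arms. The GEE interaction, the GEE main effect and the regression and mixed-model analyses in Sections 10.1 and 10.3 are supportive.

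This matches Sections 6.1.2 and 10.2. The same edit should state how participants with incomplete follow-up are classified, and name the deciding test for STI testing and PrEP awareness.

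If a repeated-measures test is preferred, use one pre-specified time-averaged arm contrast (null error 4.8–5.4% in the same runs), state how time is coded, and align Sections 6.1.2 and 10.2 with it. The interaction-then-main-effect sequence should go in either case.

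The cost is a change of wording and the IRB review that Section 11.4 requires; no new data are needed. There are two trade-offs. A significant interaction would no longer count as success. And with the Z-test, the 13-point cross-sectional difference in Section 10.2 applies instead of 8.8–11.3 points. In simulation at 13 points (240 per arm, 20% dropout, constant effect on the testing rate) the Z-test had 78–80% power and the time-averaged contrast 89–98%. The sponsor should weigh that before choosing.
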